5.1 Objective & endpoints

We wish to demonstrate the feasibility and added value of an AR based (neuro)navigation system implemented on the HoloLens for guidance during EVD placement. EVD placement accuracy will be assessed using the Kakarla scale, ranging from good (grade I) to poor (grade III) placement. These clinical outcome data will be compared to normal ranges based on historical values obtained from literature and from our institution.

Secondary endpoints:

- Improvement of user experience (intuitiveness, ergonomics, quickness; using the questionnaires in Appendix B).
- Decrease of duration of procedure compared to same procedure performed without AR (based on historical values of procedure time, recorded at our institution)
- Decrease of difference in outcome (accuracy scale) and of difference in duration of procedure between surgeons of different expertise levels compared to same intervention without AR (flattening of the learning curve)
- Improvement of clinical outcome measures with AR-assisted surgery compared to standard practice (using the scales in Appendix C)
- Improvement of pathology-specific clinical outcome measures:
 - Revision rate
 - Complication rate
 - Velocity of the decrease in ICP
 - Evolution of midline shift

Exploratory endpoints:

- Explore development and optimization of an efficient and ergonomic workflow in a well-structured pipeline (pipeline from imaging to display of holograms)
- Explore and describe necessity for continuous implementation of technical advances improving the AR experience, such as:
 - Correcting for inattentional blindness (confusion between real and virtual world),
 - Correcting for the use of historical images (i.e. updating preoperative images to better reflect the current situation),
 - Implementing marker-free navigational tracking,
 - Exploring cooperation by offering different points-of-view for multiple surgeons,
 - Explore assistance of these interventions by using telepresence,
 - ...

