No data on the accuracy of twist-drill drain placement is currently available in literature, but the overall complication rate has been reported to range from 3 to 26,9%, recurrence rate from 10 to 33% and mortality rate from 2,9 to 11,4% [43,44]. Sindou et al. also reported insufficient evacuations in 3,3 to 5,7% of the cases [43], and Weigel et al. reported a cure rate (full autonomy after surgery) in up to 88,2% of the patients [44].

In this study we aim to demonstrate that AR-assistance in EVD placement surgery increases the accuracy and clinical results, flattens the learning curve for these procedures and increases surgeon comfort by making the procedure more visual in nature. For accuracy testing, the clinically validated accuracy scales will be used to compare outcomes to historical values from literature, but also historical values from retrospective review of drain placement procedures performed previously at UZ Brussel.

2 Study Design

In order to assess the accuracy of AR in EVD placement surgery with the clinical feasibility in mind, we will sequentially recruit 10-15 patients. Adequate accuracy of registered-hologram drain placement has been demonstrated in our phantom trials, that will be continued concurrently with the clinical trial in order to optimize any technical issues, the user interface and the user experience, and to demonstrate learning-curve effect in a safe manner. Thanks to Li et al [32], the preliminary work to demonstrate the efficacy and safety of the use of the HoloLens for clinical drain placement has already been done. Prior to enrollment of these patients, the surgeons will have a brief adjustment period in which the holographic information will not be displayed on the patient but elsewhere in the field of view of the surgeon (unregistered), to adjust to the HoloLens and the use of the AR navigation interface while still adhering to the conventional drain placement methods. For the following 10-15 patients the AR overlay will be registered to and displayed on top of the patient, showing the relevant anatomy in its supposed actual location (giving the impression of “see-through vision”). This conversion not only assures optimal patient safety, but also allows us to investigate and improve upon the concurrently developed AR user-interface.

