Thus, a clinical experiment will be set up where current practice is compared to AR guidance. Minimal invasive drain placement in the CSF-space (ventricle) will be performed in standard fashion, but with the aid of a 3D model of the patient and the specific compartment to be targeted displayed in the field of view of the surgeon, either without registration to the patient (i.e. next to the patient serving as an in-room 3D visualization), or with registration to the patient (i.e. on top of the patient providing the surgeon with the impression of “see-through vision”). Results from these drain placements (accuracy being measured using clinical scales) will be compared to historical controls from literature and from our center.

In order to optimize image processing from a technical point of view (optimization of segmentation procedure), but also for the mentioned concurrent phantom trials we will also (aside from the imaging data from the prospectively included patients) use imaging (CT and MRI) data, obtained retrospectively and fully anonymized, from 20 randomly selected patients.

3 Patient selection criteria

Patients must meet all of the following recruitment criteria to be eligible for enrolment into the trial:

1. Diagnosis of any intracranial pathology requiring external ventricular drain placement.
2. Age ≥ 18 years.
3. The patient or his/her legal representative must be able to understand the planned study treatment after receiving a detailed verbal explanation, after which they had the chance to ask any remaining questions.
4. No contraindication for evaluation by CT.
5. Baseline CT is performed maximum 1 week before initiation of treatment (usually even performed at the moment of diagnosis, immediately prior to the intervention).
6. Current clinical status does not prevent the patient from undergoing the standard treatment for the abovementioned condition(s); standard inclusion and exclusion criteria for surgery in general will be applied.
7. Willingness and ability to comply with scheduled visits, treatment plans and other study procedures.
8. The patient or his/her legal representative signed and dated the **informed consent** (IC) document indicating that the patient (or legal representative) has been informed of all the pertinent aspects of the trial.

4 Treatment plan

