4.1.2 Operative phase

The procedure itself will take place in a standardized fashion, performed by surgeons (in this case neurosurgeons or neurosurgeons in training) of different expertise levels (but always with adequate expertise and clearance to perform this procedure, as is current clinical practice). Surgical technique for the procedure is described below. The main difference is the use of the HoloLens as an AR device for visual aid during the procedure, which will not alter the operational workflow. The HoloLens will only be used immediately before and during the planned surgical procedures.

Surgical technique

The patient is installed on the operating table in the supine position. Patients will be sedated. The entry point is decided by the surgeon (usually at Kocher's point), based on the pathology at hand, pre-existing anatomical knowledge and knowledge of anatomical landmarks, but also surgical planning information based on the preoperative CT scan, as well as the augmented reality-displayed surgical trajectory. The entry point is then marked on the skin (after local shaving if necessary) and the patient undergoes standard surgical prepping (disinfection) and draping. A stab incision is made at the entry point, after which the hand drill is placed against the skull and a drill trajectory is made in the skull, following the predefined trajectory that the drain should follow. This trajectory is based, again, on the pathology at hand, pre-existing anatomical knowledge and knowledge of anatomical landmarks and trajectories, surgical planning information based on the preoperative CT scan, and, importantly, the augmented reality-displayed surgical trajectory. The drain is then placed through the drill hole and advanced until the predefined depth (decided upon based on the surgical planning). After placement, flow of CSF or blood (depending on the pathology) through the drain is checked, after which it is secured to the skin with suture thread and connected to a drainage system.

Analysis

The following measures pertaining to the surgical experience will be recorded during and after the surgical procedures:

- Duration of the surgical procedure (in minutes)
- Number of passes of the drain before correct placement
- Surgeon's estimate of success of placement (using the graded scale detailed below)
- Surgeon experience (detailed questionnaire available in Appendix B)

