4.4 Life Style Guidelines

The use of the HoloLens does not interfere with the patients’ life style. Lifestyle adjustments will therefore only be adjusted if necessary based on the requirements for the planned surgical procedure. This includes the standard period of post-operative care and follow-up.

5 Statistical design

This is a class II, single-arm, clinical pilot study investigating feasibility, safety and efficacy of a proprietary software solution for augmented reality-display, and registration and tracking of patient-specific anatomic models on the Microsoft HoloLens (further referenced to in this paragraph as “the experimental treatment”) in patients requiring EVD placement.

A patient is considered evaluable if he has signed informed consent and has undergone the HoloLens-assisted surgical intervention. Primary endpoint is accuracy according to the abovementioned Kakarla scale and can be evaluated within 24 hours after surgery. Patients will be encouraged to complete follow-up (which does not differ from standard follow-up for these pathologies) in order to evaluate the secondary endpoints (clinical outcome, cfr below) but will remain evaluable in the context of the trial even if planned follow-up has not been completed.

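### The learning-curve endpoint credits any narrowing of the gap between expertise levels, including one produced only by experienced surgeons doing worse with AR

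*Combined protocol and SAP*

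**What the plan says.** The synopsis and section 5.1 give the same secondary endpoint: "Decrease of difference in outcome (accuracy scale) and of difference in duration of procedure between surgeons of different expertise levels". The reference is freehand practice, and the plan itself labels such a decrease as a flatter learning curve. Section 1.3 makes this a study aim, stating that AR "flattens the learning curve for these procedures", next to aims on accuracy, clinical results and surgeon comfort.

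The design is described in section 5: "This is a class II, single-arm, clinical pilot study investigating feasibility, safety and efficacy". Section 2 says results "will be compared to historical controls from literature and from our center". Section 4.1.2 says procedures are "performed by surgeons (in this case neurosurgeons or neurosurgeons in training) of different expertise levels", without a number of surgeons or of cases per level.

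Section 5.4 specifies one-sided Fisher's exact tests for placement accuracy with and without AR. It gives no analysis, strata or success rule for the difference between expertise levels. Section 2 adds an adjustment period with unregistered holograms before enrolment, and phantom trials that continue alongside the clinical trial, partly "to demonstrate learning-curve effect in a safe manner".

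The measures listed in section 4.1.2 include procedure duration, "Number of passes of the drain before correct placement" and the surgeon questionnaire in Appendix B.

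**The concern.** A difference between two groups can shrink from either end. The endpoint names only the shrinkage and attaches a favourable label to it. If experienced surgeons lose accuracy or time with an unfamiliar headset while juniors stay where they were, the definition is met.

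The protocol itself gives reasons to keep that possibility open: it provides a period for surgeons to adjust to the HoloLens, and it lists inattentional blindness among the matters still to be corrected.

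At stake is the interpretation of a stated aim. Section 5.2 says positive results may lead to a larger randomised trial, and a flattening claim that rests on worse senior performance could be carried into its rationale.

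A second, smaller issue is practice. The endpoint contrasts groups of surgeons at one stage; it does not follow performance over successive cases. If surgeons bring different amounts of AR practice to a case, a single-arm comparison with historical cases cannot separate that from the effect of AR.

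**Working it through.** **Plan's own figure.** None exists for this endpoint. The only calculated figure, 67 patients in section 5.2, concerns overall accuracy. It is reproduced as the per-group size for a one-sided Fisher's exact test of 80% against 95% (alpha 0.05, power 80%), but has no bearing here.

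**Inputs.**
- From the documents: 10-15 patients (5.2); pooled freehand good placement of 77-79% (1.3).
- Assumed, because the documents give no rates by expertise: freehand good placement of 85% for seniors and 70% for juniors; a historical gap of 85 − 70 = 15 points treated as known; 15 AR cases split 7 + 8, or 10 split 5 + 5; independent cases. The assumed rates pool to (7 × 85 + 8 × 70) / 15 = 77%, inside the literature range.

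**Step 1: expected values.** If seniors fall to 70% and juniors stay, the gap goes from 15 to 70 − 70 = 0. If juniors rise to 85% and seniors stay, it goes from 15 to 85 − 85 = 0. The endpoint is identical in the two cases. Pooled accuracy moves in opposite directions, from 77% to 70% and from 77% to 85%.

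**Step 2: chance of observing a smaller gap.** Let S and J be the numbers of good placements among senior and junior cases, both binomial. The signed criterion is S/7 − J/8 < 0.15. For S = 2 to 7 this is the same as J ≥ S; for S = 0 or 1 it always holds. Hence P = Σ P(S = s) P(J ≥ s) over s = 2 to 7, plus P(S ≤ 1).

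No effect (85/70), terms for s = 7, 6, 5, 4, 3 and ≤ 2:

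0.3206 × 0.2553 + 0.3960 × 0.5518 + 0.2097 × 0.8059 + 0.0617 × 0.9420 + 0.0109 × 0.9887 + 0.0013 = 0.54.

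Seniors at 70%, juniors unchanged:

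0.0824 × 0.2553 + 0.2471 × 0.5518 + 0.3177 × 0.8059 + 0.2269 × 0.9420 + 0.0972 × 0.9887 + 0.0288 = 0.75.

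The absolute criterion is |S/7 − J/8| < 0.15, enumerated in the same way. For 5 + 5 cases the signed criterion reduces to S ≤ J and the absolute one to S = J.

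| Cases, reading of the gap | No effect | Seniors fall to 70% | Juniors rise to 85% |
|---|---|---|---|
| 7 + 8, signed | 54% | 75% | 84% |
| 7 + 8, absolute | 44% | 44% | 64% |
| 5 + 5, signed | 42% | 64% | 69% |
| 5 + 5, absolute | 26% | 27% | 37% |

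**Step 3: other assumptions.** Over assumed pairs 85/70, 88/68 and 90/65 and splits 5 + 5, 7 + 8, 4 + 8 and 5 + 10, the ranges are 35-58% (no effect), 63-87% (seniors fall to the junior rate) and 69-96% (juniors rise to the senior rate) for the signed gap, and 23-57%, 27-71% and 37-90% for the absolute gap. The harmful and intended scenarios overlap.

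**Step 4: the proposed conditional rule.** Take the rule as observed junior rate above 70% and observed senior rate at least 85%. With 7 + 8 cases that means at least 6 of 8 and at least 6 of 7.
- No effect: 0.7166 × 0.5518 = 0.395.
- Seniors at 70%: 0.3294 × 0.5518 = 0.18.

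With 5 + 5 cases it means at least 4 of 5 juniors and 5 of 5 seniors.
- No effect: 0.4437 × 0.5282 = 0.23.
- Seniors at 70%: 0.1681 × 0.5282 = 0.09.

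The rule is noisy, but senior deterioration now makes the claim less likely.

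**The case against.** The best defence is that senior deterioration would show elsewhere. Accuracy is the primary endpoint and duration a separate secondary one, each compared with historical values, and section 1.3 states its aims jointly. In the illustration, pooled accuracy would fall from 77% to 70%. This stands in part. However, those comparisons are not split by expertise, the accuracy tests are one-sided towards improvement, and neither comparison is a condition for the flattening claim.

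Three stronger readings are tempting, and the documents do not support them.

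- *The endpoint succeeds more often when AR does harm.* Against no effect, this depends on the reading. It holds for the signed gap (75% against 54%), but with the absolute gap, at least as natural a reading, the figures are 44% and 44%. On either reading the intended benefit scores higher than harm.
- *The plan collects nothing on operator experience or practice.* Appendix B, invoked in 4.1.2, records resident year or year of certification, training level, surgical volume and participation in a similar study. AR case order can probably be rebuilt from surgery dates. What is missing is a count of earlier phantom and unregistered uses.
- *Phantom practice contaminates the result.* Section 2 does not say that the trial surgeons take part in the phantom trials. Carry-over is possible, not documented.

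It is also fair that this is one secondary endpoint in a small feasibility pilot, and that any replacement rule will be noisy at this size.

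**Conclusion.** The concern holds as a defect in the endpoint's definition. That conclusion follows from the wording alone: a bare decrease in a difference gives full credit to a gap closed by senior deterioration, and nothing elsewhere in the plan withholds it.

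The probabilities are illustrative. They rest on assumed rates by expertise, assumed case splits and a historical gap taken as known. They show that neither reading of the gap penalises harm to senior performance, and that 10-15 cases separate harm from benefit poorly. They do not show that harm is likely. A reader might infer that the sponsor would announce harm as success; the plan states no success rule for this endpoint, so the risk is over-interpretation of a favourable label.

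The change should be made, but the validity of the trial's primary assessment does not depend on it.

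**What to change.** 1. In section 5.1 and the synopsis, replace the gap endpoint with results by expertise level: AR accuracy and duration against institutional freehand results at the same level, with counts and confidence intervals, labelled descriptive.
2. Allow the term flattening only if junior results are better with AR than junior freehand results and senior results are not worse. State that at 10-15 patients this rule is itself noisy, citing figures such as those in step 4 with their assumptions.
3. Link the operator level already collected in Appendix B to each case, and derive the operator's registered-AR case number from surgery dates.
4. Add one eCRF field for the operator's earlier phantom and unregistered AR uses, and list cases in order of AR experience.

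The cost is an endpoint rewording, some data linkage and one new field, with no extra patients or procedures. It requires institutional freehand records that can be split by operator level. The learning-curve claim becomes harder to make and mostly descriptive.

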5.2 Sample size calculation

When aiming to objectively demonstrate an accuracy improvement of EVD placement obtained through AR guidance in comparison to the freehand technique, we'd aim for 95% correct placement

as is the case for guidance using conventional neuronavigation systems. Testing against the null hypothesis EVD placement accuracy of 70-80% with current freehand techniques, thus would be the alternating hypothesis accuracy of 95% using AR guidance. Given a significance level (i.e. the probability of rejecting H_0 when it is true) of 5% ($\alpha=0,05$) and power (i.e. $1-\beta$, the probability of confirming the added value) of 80% ($\beta=0,20$), minimally 67 patients would be needed.

However, given the purpose of the current study being the evaluation of the system's feasibility for intraoperative use in a critical care setting, this number will be limited to 10-15 patients, as is common practice for such studies. Following positive results, this trial may be followed by such a larger, randomized controlled trial. Dropout is expected to be unlikely, since the surgery is planned unrelated to the study and will not be cancelled under normal circumstances.

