The **Augmented Reality-Assisted Neurosurgical Drain placement** (ARANED) study is part of a larger project called **Surgical Augmented Reality Assistance** (SARA). The goal of the SARA project is to assess the added value of **augmented reality** (AR) during surgery in terms of usability, relevance and (surrogate) outcomes (measuring for accuracy, usefulness, gain in time, patient safety and physician comfort). To this end, a series of experiments is defined, complementary to each other, and involving a variety of medical specialties, focusing on cranial and spinal neurosurgery and orthopedic surgery. The use of the AR device with associated software will first be assessed with several preclinical experiments based on geometric models, anthropomorphic models and cadavers.

Clinical testing within the scope of the SARA project will be limited to class II pilot studies, and all procedures will take place in specific settings where the safety of the human subjects cannot be compromised. Completion of larger-scale clinical randomized trials are beyond the scope of this project.

ARANED focuses on neurosurgical drain placement. Drain placement is an often-used procedure for patients with increased intracranial pressure (**intracranial hypertension**; ICH) or with intracranial hemorrhage (**intraparenchymal hemorrhage** (IPH) or **chronic subdural hematoma** (CSDH)), with the goal to drain **cerebrospinal fluid** (CSF) or blood, respectively, as well as to measure pressure in the specific compartment the drain is positioned in. To drain CSF, a so-called **external ventricular drain** (EVD) is placed. The placement of any intracranial drain is almost always performed freehand, following inspection and planning on CT images of the patient. For EVD placement additional, literature-defined landmarks are employed, however, these are not patient-specific. As detailed below, these procedures and their accuracy have been studied extensively in literature, making them a suitable subject for clinical testing.

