Accuracy rates according to this scale have been reported in literature to be between 77 and 79% for good placement, between 10 and 14% for suboptimal placement and between 7 and 13% for poor placement using the freehand technique [35,36]. Multiple passes were reported in 5,4% of the EVD placements [36]. Similar studies have been performed when using guides or image guidance [35,36]. In literature, the overall complication rate (covering drain-related infections, post-placement hemorrhage and malplacement of the ventricular drain) ranges from 14,2 to 16,1% [36,37]. Hemorrhage has been reported to range from 1,8 to 33% [35,37,38], and reported infection rates range from 5,4% to 10,2% [36,37]. Kakarla et al. reported a mortality rate of 0,6% [35].

For intra-hematoma drain placement for IPH, a scale defined for the MISTIE trial [39] is used (*Table 2-2*):

Assessment	Description
Good placement	Placed along the entire longitudinal axis of the hematoma with the fenestrated segment in the epicenter of the clot, circumferentially surrounded by the hematoma
Suboptimal placement	Over- or undershooting the target position or in eccentric location, yet fully engaging the IPH and suitable for dosing
Poor placement	Not engaging the IPH (i.e. catheter perforations not in contact with the clot), not allowing safe/effective dosing, hence requiring replacement

Table 2-2. Accuracy scale for drain placement in an IPH

Literature reports that for IPH drainage using catheters, 58% of drains is in good position, 28% is suboptimally placed (but sufficient for drainage and intra-hematoma administration of specific drugs), and 14% is poorly placed (requiring repositioning) [40]. The overall complication rate goes up to 33,3% [41,42] and Barrett et al. also reported a mortality rate of 13,3% [42].

For twist-drill drainage of CSDH, [43] no specific scale has been described so far. For consistency with the abovementioned scales, we suggest the following classification (*Table 2-3*):

Assessment	Description
Good placement	Drain positioned in the hematoma in the subdural space
Suboptimal placement	Placement in the subdural space but not in the hematoma
Poor placement	Incorrect placement of the drain: subcutaneous placement, epidural placement or intraparenchymal placement of the drain

Table 2-3. Accuracy scale for drain placement in a CSDH

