5.4 Statistical analysis

Dichotomized comparisons will be used to compare drain placement accuracy performed with versus without surgical AR assistance. Results obtained from the Kakarla scale after surgery with the AR guidance will be tabulated and compared to historical values obtained from literature and from our institution. These historical values are based on previous research in drain placement (without the use of AR guidance), and will be matched with the cases of the current study.

To achieve these dichotomized comparisons, we will use cut-offs within the accuracy scale to define different benchmarks of good versus bad drain placement. The cut-off can be placed at either side of the 'suboptimal placement'-category (cfr. Part 1), depending on the degree of accuracy we wish to pursue: a comparison with the cut-off above this category will analyze the improvement of perfect placement, whereas the cut-off below this category will analyze acceptable drain placement in general. Given the eventual alternating hypothesis of increased placement accuracy related to the use of AR guidance, along with the small expected sample size, these comparisons will be performed through one-sided Fisher's exact tests.

6 Patient registration procedure

Prior to undergoing any study-specific procedure, patients must read the patient information brochure and sign the current **Institutional Review Board** (IRB)-approved IC form (see Part 10.3 for the procedure during emergency situations). Screening procedures can then take place as listed in Part 4. Subjects meeting the eligibility criteria for study participation will start experimental treatment as soon as is estimated possible by the investigator.

Patient withdrawal

A patient may withdraw from the trial at any time at their own request, or they may be withdrawn at any time at the discretion of the investigator or sponsor for safety, behavioral, or administrative reasons. Unless the subject specifically withdraws his consent for use of the obtained data, the patient will remain evaluable within the trial if he has undergone the AR-assisted surgical procedure since the primary endpoint and some secondary endpoints are based on results that are obtained immediately after the surgical intervention.

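### Does the unlabelled figure of 67 patients in section 5.2 make the sample size calculation wrong?

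*Combined protocol and SAP*

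**What the plan says.** Section 5.2 sets up a comparison of AR guidance with freehand placement: "Testing against the null hypothesis EVD placement accuracy of 70-80% with current freehand techniques", an alternative of 95%, 5% significance and 80% power. It concludes that "minimally 67 patients would be needed". It then sets this figure aside because the study is about feasibility: "this number will be limited to 10-15 patients, as is common practice for such studies". It adds that, if results are positive, "this trial may be followed by such a larger, randomized controlled trial".

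Three other places bear on the point:

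- Section 1.3 cites freehand accuracy "between 77 and 79% for good placement".
- Section 5.4 says of the pilot's comparisons with historical values that, "along with the small expected sample size, these comparisons will be performed through one-sided" Fisher's exact tests. It says of those historical values that they "will be matched with the cases of the current study".
- The opening summary states: "Completion of larger-scale clinical randomized trials are beyond the scope of this project".

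**The concern.** One number is given for a null range ten points wide, and five inputs are left out: per group or total, the null value, the test, its sidedness and the allocation ratio. The neighbouring sentences pull in different directions. Cutting the number down to 10-15 patients suggests that 67 counts AR-treated patients, because the pilot has a single arm. Pointing to a later randomised trial of that larger kind suggests that 67 is the size of a two-arm trial.

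A reader who takes the sentence at face value may read 67 as a total. A follow-on trial built on that reading could be badly underpowered at the freehand rate that the protocol itself cites.

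**Working it through.** **Inputs.** From section 5.2: AR rate 95%, freehand rate p0 of 70-80%, significance level 0.05, power 0.80, no dropout allowance. From section 5.4: one-sided Fisher's exact test. Assumed: this test also underlies the 67, and allocation is 1:1.

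**Formula.** With n_C freehand and n_A AR patients, and x and y good placements in each,

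power = Σ_x Σ_y Bin(x; n_C, p0) · Bin(y; n_A, 0.95) · 1[p(x, y) ≤ 0.05],

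where p(x, y) is the upper hypergeometric tail: the chance of y or more good placements in the AR group given x + y in total. The sums run over all outcomes, so the power is exact.

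**Step 1: reproduce 67.** At p0 = 80%:

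- 66 per group: power 79.96%
- 67 per group: power 80.60%

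So 67 is the smallest group size that reaches 80%, or 2 × 67 = 134 patients in total.

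**Step 2: try 67 as a total.** At p0 = 70%, 33 per group gives 79.97% and 34 per group gives 81.5%, so equal groups need 2 × 34 = 68. A 33/34 split of 67 patients gives 82-83%, depending on which arm has 34. This reading therefore also fits, but only at the low end of the null range.

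**Step 3: try 67 as a single arm.** An exact one-sided binomial test against a fixed 80% holds 80% power from n = 37 and has 98% power at n = 67. A one-sample test does not explain the figure.

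**Step 4: power of the two readings across the null range.**

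| Freehand rate | 67 per group | 67 in total (33/34) | Smallest n per group (total) |
|---|---|---|---|
| 70% | 98.7% | 82-83% | 34 (68) |
| 75% | 94.2% | 66-68% | 45 (90) |
| 77% | 90.2% | 58-61% | 52 (104) |
| 79% | 84.4% | 49-52% | 61 (122) |
| 80% | 80.6% | 45-48% | 67 (134) |

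As a total, 67 drops below 80% power once the freehand rate passes about 71%.

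**Step 5: look for any use of 67 in this study.** Section 5.2 replaces it with 10-15 in the next paragraph. The definition of an evaluable patient at the start of section 5, the accrual rules in 5.3 and the comparisons in 5.4 do not refer to it. No stopping rule or success criterion is tied to it.

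**The case for a change.** The strongest case for a change is that a stated sample size should be reproducible without guessing. Section 5.2 offers 67 as the size that a confirmatory comparison would need, so a later team may well reuse it. If they take it as a total, they would run at about 49-61% power at the cited 77-79%. Sidedness adds to this: with a two-sided 5% test, 67 per group gives only 70% power at an 80% freehand rate, and 82 per group would be needed.

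The omission is real, and so is the risk of misreading. Section 5.4 does not settle the matter either, because it names its test for the pilot's comparisons and 5.2 does not refer to it. But these figures show what would follow from a particular misreading or a different choice of test. They do not show that 67 is wrong. The two-sided case assumes something that the documents nowhere state; the only sidedness they give is one-sided. A later randomised trial would need its own protocol and its own calculation, with its own control rate and test.

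**Conclusion.** No change is needed. The number is incompletely labelled but not shown to be in error. Under the one test that the document names, it is exactly the per-group minimum for 80% against 95%. That takes the most demanding end of the null range and keeps power between 80.6% and 98.7% over the rest of it. The total reading works only up to a freehand rate of about 71%, and the text does not establish that it was meant.

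This rests on two assumptions: that the one-sided Fisher test of section 5.4 underlies the 67, and that allocation is 1:1. The derivation is therefore inferred; the power figures are exact once those assumptions are granted.

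Whichever reading was intended, the difference of 67 patients (134 − 67) concerns only a possible later trial. The pilot's enrolment, its analysis and the conclusions it can support are the same either way, so writing out the derivation would gain this study nothing.
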